🛛 Data	and Safety Monitoring Plan
🗌 Depa	rtment of Corrections application
🗌 Docu	mentation that the product is an approved food additive (21 CFR 172)
🗆 Exter	nal IRB document(s)
🗆 Exter	nal study document(s)
🗆 FDA (Correspondence
🗆 FDA '	'Safe to Proceed" letter
\Box GMP	certificate or food-grade certificate that indicates that the product can be lawfully used in the US food supply
🗌 Grant	or contract if not already in Cayuse
🗆 IND c	r IDE Application for Investigational New Drug or Device
🗆 Inves	tigator brochure
🛛 Label	for investigational drug or device
🗆 Lette	r from the FDA or industry sponsor setting forth the IND number
🗆 Lette	r(s) of support or permission
🗆 Packa	ige insert
🛛 Recru	itment materials
🛛 Refer	ences or citations
□ Safet	y data if GRAS status is self-affirmed
⊠ Scree	ning or eligibility checklist(s) or document(s)
🗆 Surve	ys, questionnaires, interview or focus group guide(s)
□ Trans	lated document(s)

□ Tribal Council Resolution or other appropriate supporting documentation from the appropriate Tribal authority

Additional attachments:
🖾 Food Diary
⊠ Demographics form
Health assessment form
⊠ Cruciferous vegetable list

PI should email completed application and all relevant attachments to [contact]

Statistical Analysis Plan

Pharmcokinetic parameters were evaluated for linearity using a best fit modeling approach. First, pharmacokinetic parameters were evaluated for significant change as a functin of dose using a standard linear regression model including a fit y-intercept. Slopes were compared using a *t*-test and an alpha value of 0.05. If the parameter changed as a function of dose, we further evaluated the parameter with a linear regression model, with *k* as the slope through the origin and a Michaelis-Menten model, which assumes saturation at V_{max} and an affinity constant K, to individual parameters (p) as a function of extermal [¹⁴C]-BaP dose. The Baysesian information criterion (BIC) was used to judge the best-fit model and provide evidence of linear or saturable pharmacokinetics.

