Our hypothesis is that micro-dosing with a binary mixture of [¹⁴C]-BaP and another PAH will result in no change in plasma and urine [¹⁴C]-BaP metabolites, the [¹⁴C]-BaP Cmax in blood or the rate of elimination. This hypothesis will be tested by micro-dosing individuals with a binary mixture of [¹⁴C]-BaP and non-radioactive phenanthrene. We will dose individuals with 50 ng of [¹⁴C]-BaP alone and, following a washout period, previously shown to reduce [¹⁴C]-BaP levels in plasma and urine to levels below detection (<1 fg/mL), compare to a binary mixture of 50 ng [¹⁴C]-BaP and 1250 ng of non-labeled phenanthrene (non-carcinogenic PAH²), a BaP:phenanthrene ratio commonly found in food⁵. The determination of the effect of phenanthrene on uptake, metabolism and elimination of [¹⁴C]-BaP will test a basic tenet of the Relative Potency Factor (RPF) approach to risk assessment (proposed by the U.S. EPA) for PAH mixtures⁶, that there is no impact of a PAH on the pharmacokinetics of another PAH (i.e. the cumulative risk is additive).

To date, our accelerator mass spectrometry (AMS) studies with PAHs have employed a single PAH given at a single dose^{7,8}. We have chosen to employ a simple binary mixture as the simplest model to test the assumption that one PAH will not impact the kinetics of another PAH. Phenanthrene is an excellent choice as 1) it is a major component of environmental PAH mixtures^{1-5,9, 2}) it contains a bay region as does BaP and is thus metabolized in a similar fashion¹⁰, 3) it has been evaluated by IARC and EPA and considered not to be a carcinogen (IARC class 3, EPA RPF of 0)^{2,4,6} and 4) it has been previously employed safely in FDA-approved clinical trials in humans at a dose 10,000 ng¹¹. Thus, this will be the first actual test of the RPF approach to risk assessment via micro-dosing in humans of a defined binary mixture of a carcinogenic (BaP) and non-carcinogen (phenanthrene) PAH. For non-cancer risks, the EPA has set a safe lifetime **exposure** value of 40,000 ng/Kg/day⁶, a value more than 2,200 time greater than the single phenanthrene dose (1250 ng/70 Kg) proposed here.

Pharmacokinetic parameters for [14C]-BaP and metabolites, in the presence and absence of co-

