administration with phenanthrene, will be assessed by ULPC-AMS in plasma and urine collected over 48 hours. Metabolite profiles and kinetics of elimination over this dose range are predicted to be consistent with the BaP PBPK model developed by our present and past collaborators at Pacific Northwest National Laboratory (PNNL)¹². The results from this study will be disseminated in peer-reviewed toxicology/environmental health journals, at scientific meetings and provided to the U.S. EPA for incorporation into their risk assessment models. The experimental procedure employs accelerator mass spectrometry (AMS) for analysis. AMS (10³-10⁹ more sensitive for ¹⁴C than scintillation counting) is increasingly used to determine pharmacokinetics of drugs under development. A dose given to human volunteers of no more than 1/100 the expected therapeutic dose, or less than 100 µg of [¹⁴C]-labeled drug (usually 100-200 nCi), is referred to as "microdosing" (Phase 0 studies or eIND studies). This approach has been validated for exploratory clinical development by the Consortium for Resourcing and Evaluating AMS Microdosing (CREAM Trial) and the EU Microdosing AMS Partnership Programme (EUMAPP). This early use of human subjects in drug development is consistent with the goals of the FDA Critical Path Initiative and AMS in exploratory IND applications has been addressed by FDA¹³. AMS has been used in toxicology and carcinogenesis studies. AMS sensitivity allows the study of pharmacokinetics and DNA binding of environmental contaminants known to be animal carcinogens and suspected of being human carcinogens including the cooked meat mutagens PhIP and MeIQx, the mycotoxin and human hepatocarcinogen AFB₁, in addition to BaP¹⁴. It is noteworthy that our group has successfully completed AMS studies with AFB₁ and the PAH, dibenzo[def,p]chrysene (DBC)^{7,8,15}. IARC estimates that a non-smoker, not exposed occupationally, will receive a daily dose of 270-700 ng of BaP; about 95% through the diet². The European Union maximum limit for BaP in fish is 2,000 ng/Kg f.w. and the FDA Limit of Concern (LOC) is 35,000 ng/Kg. The dose of 50 ng would be the equivalent of eating 25 or 1.4 g of fish at the EU, and FDA limits, respectively. The World Health Organization has set an estimated safe daily lifetime (70 years for a 70 Kg individual, cancer endpoint) exposure to BaP of 42-350 ng⁹. With respect to the internal dose of [¹⁴C] of 5.4 nCi, this represents 0.6% the dose given in a common diagnostic procedure (¹⁴C-urea test for Helicobacter)¹⁶ and 4 and 5 orders of magnitude lower than a recently published paper dosing people with 300 μ Ci of epicatechin¹⁷. Therefore, from the standpoint of both chemical and radioisotope dose to the volunteers, this protocol represents de minimus risk and that was the finding of the FDA (IND 117175) in a "study may proceed" determination for our IRB protocol 5644 which uses a dose of 46 ng (5 nCi).

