	Previously, the oral exposure slope factor for cancer risk (70 years, 70 Kg adult) for BaP using a linear, non- threshold model (EPA-IRIS) was 7.3 mg/kg-day ⁻¹ , but EPA recently lowered this to 1 mg/(kg-day) ⁴ . Cal/EPA uses a safety factor for age sensitivity (2.9 mg/kg-day ⁻¹). This risk assessment is based on high dose (1-100 mg/kg-day) exposures in rodents- 5-6 orders of magnitude higher doses than human exposures . This risk assessment may not adequately protect some populations. Studies, including our own, with PAH mixtures indicate the linear extrapolated dose may under-estimate actual human risk using the Relative Potency Factor (RPF) approach ⁶ . The RPF approach assumes linear pharmacokinetics for PAHs and their metabolites with dose but this has never been assessed in humans. With the common PAH phenanthrene, a non- carcinogenic PAH, we can test the additivity assumption of the RPF approach in the simplest (binary) mixture possible and at a ratio of the 2 PAHs present in diet.	
	Our preliminary results show the plasma level, as determined by AMS at Crew (highest concentration	

	obtained) after dosing individuals with 46 ng [¹⁴ C]-BaP, was ~ 8 fM (femto(10 ⁻¹⁵ moles/L)) ²⁰ , or 10⁷ lower than an in vitro study (50 nM) showing no adverse impact on hepatocytes. The sensitivity of AMS allows for micro-dosing with [¹⁴ C]-BaP in humans with de minimus risk to determine [¹⁴ C]-BaP and individual metabolites in the low fM range (2-20 femtograms/mL plasma). Our premise is- the best model for humans is humans. Utilizing PBPK models, we can provide a much more accurate estimate of BaP levels in human tissues following exposure at environmental levels as well as individual metabolites representing reduced or enhanced risk.			
1	Background justification should support the objectives of the research as well as the knowledge that is anticipated from the research results. Explain the need for the study and what gap in knowledge the results are expected to fill. Summarize relevant existing data, literature, past and ongoing studies, and how your study ties in with these. Provide specific methods and procedures in a later section.			
4	Is the study student-driven (for the purpose of a thesis, dissertation, or other)?		\boxtimes	
SECTION 14 - Target Enrollment		Yes	No	N/A
1	What is the target enrollment number?			
	Up to 50 people will be enrolled in this study. Our goal is for 7 subjects to complete the study.			

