	within the prior 12 months. These subjects will only complete 2 food diaries (3 days prior to the cycle and during the 48-hour cycle). Studies to date have shown little intra-individual variation in [¹⁴ C]-BaP pharmacokinetics with time (at least up to 12 months) between doses. ²⁰		
	Subjects will be asked to defer blood donation for one month before, throughout, and for one month after completion of the study. At any point during the study, subjects will be referred to their physician if the study physician or nurse consider this advisable.		
	Processing of samples:		
	Blood samples will be centrifuged to obtain plasma and peripheral blood mononuclear cells (PBMCs). The [¹⁴ C]-BaP and metabolites will be extracted directly from plasma by liquid/liquid extraction with ethyl acetate. The urine will be pooled over the time periods pre-capsule (baseline), 0 – 12, 12-24, and 24-48 hours. After volumetric quantitation of each pool of urine, 12 mL will be collected, 4 mL will be adjusted to pH 5 and half treated with β -glucuronidase/sulfatase prior to extraction with ethyl acetate. The plasma and urine extracts will be blown down under argon, sealed in amber vials and shipped to LLNL where they will be injected onto an Ultra-Pressure Liquid Chromatograph (UPLC) interfaced via a "moving wire" into the AMS ¹⁹ . We will be able to determine femto(10 ⁻¹⁵)g/mL levels of BaP and BaP metabolites (by co-elution with unlabeled standards available from the OSU Superfund Research Center PAH repository). The time-course of blood and urine levels of parent BaP and metabolites will be used to construct a pharmacokinetic model ¹² . In addition, DNA isolated from PBMCs at 0 hr and 48 hr will be counted directly on the AMS to check for levels of covalent DNA binding.		
0	If the study involves accessing student education records, list all data to be used (e.g. course grades, assignments, GPA, video-recordings of class activities, etc.)		
0	Identify any surveys or questionnaires that are being tested or validated instruments that have been modified for the purposes of this study.		
0	Identify any novel or modified experimental activities that are being tested the purposes of this study.		
0	Specific information related to the use of drugs, devices, biologics, food, biospecimens, and radiation will be requested later in this document.		
2	If any of the activities would be conducted regardless of the research, briefly describe those activities here:	\boxtimes	

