1	Are one or more drugs or biologics being studied as part of this project?		□ Skip to section 25	
2	Drug Name (include generic and trade name, if applicable):			
	[7- ¹⁴ C]-benzo[a]pyrene (BaP), specific activity 27 μCi/μmol			
3	Approval Status (e.g., FDA Approved, FDA Approved/Unapproved Use, not FDA approved):			
	not approved for therapeutic use; this protocol is an amendment to FDA IND 117175 (see IRB Protocol 8233 for FDA correspondence)			
4	Has an IND application been submitted to the FDA?	\boxtimes		
5	If no, provide justification:			
6	Chemical formula:			
	C ₂₀ H ₁₂			
7	Dosage strength(s):			

	50 ng (alone or with 1250 ng phenanthrene)		
8	Rationale for choosing the drug or substance dose:		
*	The U.S. EPA is considering a model of risk assessment for PAH mixtures that utilizes the Relative Potency Factor (RPF) approach, derived from animal studies ⁶ . BaP is the reference compound and has an RPF of 1. The accuracy of the RPF approach is based on the assumption that the interaction between all PAHs is additive (same Mechanism of Action or MOA) and that high-dose animal data can model human exposure at environmentally relevant levels (orders of magnitude lower than the animal studies). Until now, it has not been possible to test these caveats in humans. The administration of the binary mixture of [¹⁴ C]-BaP plus phenanthrene will allow us to better determine PAH risk assessment and pharmacokinetics at environmentally relevant levels of exposure in humans.		
9	Method/route of administration:		
	Subjects will consume one capsule containing either [¹⁴ C]-BaP alone or [¹⁴ C]-BaP plus phenanthrene by mouth with 100 mL of water.		
10	Mechanism of action:		

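### The SAP tests for change with BaP dose, which is 50 ng in both cycles; it has no mixture-versus-alone contrast and no rule for concluding no change

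*Combined protocol and SAP*

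**What the plan says.** Section 13 (Study Overview, item 1) hypothesises that micro-dosing labelled BaP with "another PAH will result in no change in plasma and urine" BaP metabolites, in blood Cmax or in the rate of elimination. It presents this as a test of the Relative Potency Factor (RPF) tenet that one PAH does not alter the pharmacokinetics of another. The results are to be "provided to the U.S. EPA for incorporation into their risk assessment models".

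Section 24 (item 7) gives the dosage strength as "50 ng (alone or with 1250 ng phenanthrene"). Section 20 describes two cycles per subject, BaP alone and BaP plus phenanthrene. Subjects who completed the 50 ng cycle of protocol 8233 within the previous 12 months do only the mixture cycle. Section 14 states: "Our goal is for 7 subjects to complete the study".

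The Statistical Analysis Plan is a single paragraph. Its first step reads: "pharmacokinetic parameters were evaluated for significant change as a functin of dose using a standard linear regression model", with a fitted intercept. Slopes are tested at alpha 0.05. If a parameter changes with dose, a line through the origin and a Michaelis-Menten curve are fitted "to individual parameters (p) as a function of extermal [¹⁴C]-BaP dose", and BIC decides between linear and saturable kinetics. The paragraph does not mention phenanthrene, the mixture, the cycle, pairing within subject, a main parameter, a margin or a confidence interval.

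**The concern.** The analysis and the hypothesis do not meet. The SAP asks whether BaP kinetics are linear in BaP dose, and a study with one BaP dose cannot answer that. The question the study was designed to answer, the effect of adding phenanthrene, has no analysis.

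The hypothesis is also one of no effect. Supporting it requires a statement of how large an effect the data rule out. The SAP gives no such criterion and does not say how a non-significant result will be read.

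The findings are meant for regulatory risk models. If the SAP is followed, there is no result on the mixture question. If a contrast is substituted later, the parameter, scale, pairing and margin all remain open after the data are seen.

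**Working it through.** **Inputs from the documents.** BaP dose 50 ng in each cycle (Sections 13, 20 and 24); 7 completers (Section 14); alpha 0.05, sidedness not stated (SAP). There is no power, effect size, SD or margin, so the target of 7 cannot be reproduced. Section 14 justifies the enrolment number by screen failure alone.

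**Step 1: the SAP as written.** There are 7 × 2 = 14 subject-cycles, all at 50 ng.

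- Slope: Sxx = Σ(50 − 50)² = 0. The design matrix [1, dose] has rank 1 of 2, so the slope and its t-test do not exist.
- Through-origin line: the fitted value is 50k, a single mean.
- Michaelis-Menten: the fitted value is 50·Vmax/(K + 50), again a single mean. Its Jacobian has rank 1 of 2, so Vmax and K cannot be separated.
- BIC: both curves fit the same mean with the same residuals, so the data cannot tell linear from saturable kinetics.
- A 0/1 mixture indicator gives rank 2 of 2. The design can estimate the needed contrast; the SAP omits it.

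This step needs no assumption.

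**Step 2: if the 5% test were moved to the paired contrast.** Assumptions: log-normal parameters, paired t-test, two-sided 5%, n = 7, df = 6. Section 20 offers only "Studies to date have shown little intra-individual variation in" BaP kinetics, without a figure, so within-subject CVs of 10% to 40% are assumed.

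- se = √(2·ln(1 + CV²)/7). At CV 20%: √(2 × 0.0392/7) = 0.106.
- Power comes from the noncentral t with noncentrality |ln(ratio)|/se and critical value 2.447. At CV 20% and ratio 1.25: 0.223/0.106 = 2.11, power 0.426, so 57% of trials miss the change.
- 90% CI at an observed ratio of 1: exp(±1.943·se). At CV 20%: exp(±0.206) = 0.81-1.23.

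| Within-subject CV | 10% | 15% | 20% | 30% | 40% |
|---|---|---|---|---|---|
| se (log scale) | 0.053 | 0.080 | 0.106 | 0.157 | 0.206 |
| True 25% rise missed | 7% | 35% | 57% | 78% | 85% |
| True 25% fall missed | 1% | 15% | 38% | 66% | 78% |
| Rise detectable with 80% power | 20% | 31% | 43% | 70% | 100% |
| 90% CI at observed ratio 1 | 0.90-1.11 | 0.86-1.17 | 0.81-1.23 | 0.74-1.36 | 0.67-1.49 |

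A miss becomes more likely than a detection above a CV of 18% (rise) or 23% (fall).

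**Step 3: an interval rule on the same data.** No change is claimed only if the 90% CI lies inside the range. Results are from simulation (2 million trials), per parameter.

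| Within-subject CV | 10% | 15% | 20% | 30% | 40% |
|---|---|---|---|---|---|
| Claim made, true ratio 1, range 0.80-1.25 | 96% | 60% | 26% | 4% | 1% |
| Claim made, true ratio 1, range 0.67-1.50 | 100% | 99% | 91% | 50% | 20% |
| Wrong claim, true ratio 1.25, range 0.80-1.25 | 5% | 5% | 4% | 2% | 1% |

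The interval rule holds a wrong claim at the edge of the range to at most 5% whatever the CV. Non-significance gives no such protection: its error rate is the miss rate in Step 2.

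**The case against.** The strongest points on the other side are these.

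- *Dose linearity is also an RPF assumption.* Section 13 (item 3) says so, and doses pooled from protocol 8233 could inform it. That is true, but the SAP states no pooling, Section 12 limits this protocol to Aim 2 of the grant, and Section 13 (item 1) defines the tenet under test as no effect of one PAH on another. Linearity cannot stand in for that.
- *The comparison is already named.* Section 13 says the two conditions will be compared and lists the parameters. That states an aim; no statistical method follows it.
- *Dose might mean phenanthrene dose.* The SAP names labelled BaP dose. Even on the other reading, the pairing and a criterion for no change are missing.
- *The power figures criticise a test that the SAP does not propose, using assumed CVs.* This is fair. They are conditional, and the protocol's remark on low variability favours the low end, where a plain test misses little. The Step 1 defect does not depend on them.
- *The SAP is in the past tense, as if the analysis had been done.* This does not supply the missing contrast. It does bear on whether a range can still be set blind to the data.
- *The ratio carries a period effect.* Section 13 puts BaP alone first, and carried-over subjects use an earlier cycle from another protocol. This stands as a limitation of the design, to be reported with the result.
- *The remedy has limited power and leaves metabolites descriptive.* This also stands. If Cmax and elimination rate were independent (an assumption), both would fall inside 0.80-1.25 about 0.60² = 36% of the time at CV 15%, and 0.26² = 7% at CV 20%.

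**Conclusion.** The concern holds and must be fixed. The analysis is wrong for this design, not merely short on detail: the only tested quantity is a slope on a regressor that does not vary, and the hypothesised comparison has no analysis. This rests on the documents alone.

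The absence of a criterion for no change is equally plain from the text. Its practical size depends on a within-subject CV that the documents do not give. At CV 10% a plain paired test with 7 completers would rarely miss a 25% change. At CV 30% it would miss a 25% rise in about 78% of trials. At any of these CVs, non-significance alone does not show no change.

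**What to change.** Replace the dose-slope paragraph in the SAP with the following.

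1. **Estimand and analysis.** The within-subject geometric mean ratio (mixture/alone) from log-transformed parameters, with a 90% CI. BaP Cmax and rate of elimination are the main parameters; AUC0-48 may be added. For subjects from protocol 8233, their 50 ng cycle there is the alone value.
2. **Decision rule.** Claim no change for a parameter only if its CI lies inside a range stated in advance and justified by the investigators for risk assessment (0.80-1.25 is only an example). Otherwise, report the size of interaction not excluded.
3. **Metabolites.** Label these comparisons descriptive, and do not extend a no-change claim to them.
4. **Precision.** Keep n = 7 and state the precision it gives, using the within-subject CV from the earlier protocols.
5. **Transparency.** Report the fixed cycle order and the use of earlier cycles as limitations. If any outcome data have been seen when the range is set, say so.

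The cost is wording: no extra subjects or samples. The downside is that the result may be inconclusive, most likely with a narrow range and a CV of 20% or more. For comparison, 80% power to conclude no change within 0.80-1.25 at a true ratio of 1 would take 6, 10, 15, 32 or 53 completers at CV 10%, 15%, 20%, 30% or 40%. The range should therefore be chosen with the earlier CV in hand, but on risk-assessment grounds.

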Blood will be sampled at 0, 0.25 0.5, 1.0, 1.5, 2, 3, 4, 8, 24, and 48 hours (11 draws total, 8-9 of which come from the catheter). The catheter will remain in place for blood draws through hour 4. After the 4-hour blood draw, subjects will have the choice of having the catheter removed and returning for the 8 hour blood draw by straight stick, or they can keep the catheter in place and remain on-site until after the 8 hour blood draw. The subjects will be monitored by the nurse coordinator between IV blood draws. The 8 (possibly), 24, and 48 hour blood draws will be done with straight stick phlebotomy. No more than three (3) skin punctures will be made in an attempt to draw blood at each visit. The first blood draw of each cycle will be 20 mL and then subsequent blood draws will be 10 mL for a total amount of 120 mL (8 tablespoons) per cycle.

Subjects will be instructed to collect all urine during the entire 48-hour study cycle in containers provided by the study team. Subjects will be provided a discrete soft-sided cooler bag to store collected urine samples. They will be instructed to store samples at room temperature between visits and to return any filled containers at their next visit. The longest subjects will need to store samples between visits is 24 hours between Visits 3 and 4.

Two hours after swallowing the capsule, a standardized breakfast will be provided, after which subjects may resume normal eating and drinking. Packaged snacks or juice will be provided prior to the standardized breakfast if the study team determines it is necessary.

This process will be followed for [¹⁴C]-BaP alone and [¹⁴C]-BaP plus phenanthrene for a total of 2 cycles per subject. There will be at least three weeks' washout period between cycles. Previous multiple micro-dosing of the same individual has shown that after 3 weeks there is no detectable [¹⁴C] in plasma or urine, validating the choice of 3 weeks as adequate for a "washout period"^{7,8}. Extending the washout period will not adversely impact the data collected from the subjects but will minimize the subject's exposure to PAHs.

Subjects who have participated in IRB protocol 8233 (Benzo[a]pyrene Ultralow Dose-Response Study) will participate in only the [¹⁴C]-BaP plus phenanthrene cycle if they have complete the 50 ng [¹⁴C]-BaP cycle

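### The SAP's only significance test has no subject term and a regressor that does not vary, so it cannot deliver the within-subject phenanthrene comparison the study is built on

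*Combined protocol and SAP*

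**What the plan says.** The Statistical Analysis Plan is one paragraph. Pharmacokinetic parameters are first "evaluated for significant change as a functin of dose using a standard linear regression model including a fit y-intercept". It adds: "Slopes were compared using a *t*-test and an alpha value of 0.05". Only if a parameter changes with dose does a second step follow, in which a line through the origin and a Michaelis-Menten curve are fitted "as a function of extermal [¹⁴C]-BaP dose". BIC "was used to judge the best-fit model and provide evidence of linear or saturable pharmacokinetics". The paragraph names no subject effect, no pairing and no phenanthrene term.

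The protocol describes a different comparison. Section 13 (Study Overview) states the hypothesis that adding phenanthrene leaves BaP metabolites, Cmax and elimination rate unchanged. It tests this by giving the same people BaP alone and then, after washout, BaP with phenanthrene. Section 24 (Drugs or Biologics) lists the dosage strength as "50 ng (alone or with 1250 ng phenanthrene". Section 20 (Methods and Procedures) has the process followed for both conditions "for a total of 2 cycles per subject". Subjects who completed the 50 ng BaP cycle of protocol 8233 within the prior 12 months do only the mixture cycle here. In support, Section 20 says: "Studies to date have shown little intra-individual variation". Section 14 (Target Enrollment) says: "Our goal is for 7 subjects to complete the study".

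**The concern.** The value of this design lies in each subject being their own control. With 7 completers, and with the protocol itself relying on stable kinetics within a person, most of the available precision comes from cancelling the differences between people. A standard regression with an intercept and no subject term does not cancel them. It treats a subject's two cycles as two unrelated observations.

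Two faults are stacked. The regressor named cannot carry the comparison, because BaP dose is the same in both cycles. If only that is repaired, by substituting phenanthrene dose, the error term is still wrong for paired data. The stake is a phenanthrene effect of moderate size that the data could have shown but the test misses. Section 13 says the results will go to the U.S. EPA for its risk assessment models.

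**Working it through.** **Inputs from the documents.** 7 completers; 2 cycles each; BaP 50 ng in both cycles; phenanthrene 0 or 1250 ng; alpha 0.05 (sidedness not stated, two-sided assumed). The documents give no SD, correlation, effect size or power, so there is no stated figure to reproduce.

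**Step 1: the model as written.** With an intercept and BaP dose as columns, all 14 rows (7 × 2) read (1, 50). The design matrix has rank 1 and Σ(x − x̄)² = 0, so the slope and its t-test do not exist. This is so whether slopes are compared with zero or between conditions. A 50 ng BaP-alone cycle taken from protocol 8233 changes nothing, because its dose is also 50 ng.

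**Step 2: predictor recoded to phenanthrene 0 versus 1250 ng.** The slope t-test is then the unpaired two-sample t-test on 2n − 2 = 12 df. Write s_b and s_w for the between- and within-subject log SDs, and ρ = s_b²/(s_b² + s_w²).

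- SE used by the unpaired test: √[(2/n)(s_b² + s_w²)]
- SE of the within-subject contrast: √(2/n) · s_w
- Ratio of the two: 1/√(1 − ρ)

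**Step 3: size and power.** The SDs are assumptions. Each cell is 400,000 simulated trials of 7 pairs on the log scale. Rejection rates are unpaired / paired.

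| s_b, s_w | ρ | No effect | True ratio 1.5 | True ratio 2 |
|---|---|---|---|---|
| 0.3, 0.15 | 0.80 | 0.1% / 5% | 60% / 99% | 99% / 100% |
| 0.3, 0.25 | 0.59 | 0.7% / 5% | 42% / 72% | 93% / 99% |
| 0.5, 0.15 | 0.92 | 0.01% / 5% | 16% / 99% | 73% / 100% |
| 0.5, 0.25 | 0.80 | 0.1% / 5% | 14% / 72% | 63% / 99% |
| 0.2, 0.3 | 0.31 | 2.4% / 5% | 49% / 56% | 94% / 95% |
| 0.15, 0.4 | 0.12 | 3.9% / 5% | 37% / 36% | 81% / 77% |

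Check on the paired column at ratio 1.5: the noncentrality is ln 1.5 / (s_w √(2/7)). This is 0.405/0.0802 = 5.06 for s_w = 0.15 and 0.405/0.1336 = 3.03 for s_w = 0.25. The noncentral t on 6 df gives 98.6% and 71.6%, which agrees.

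**Step 4: interval width.** At SDs 0.5 and 0.15, the 95% limits on the ratio are:

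- Unpaired: exp(2.179 × √[(2/7)(0.25 + 0.0225)]) = exp(0.608), or ×/÷ 1.84
- Paired: exp(2.447 × √(2/7) × 0.15) = exp(0.196), or ×/÷ 1.22

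**Step 5: where pairing stops helping.** The two intervals are equally wide when 1 − ρ = (2.179/2.447)² = 0.793, so ρ ≈ 0.21. Below that, the lost df outweigh the variance removed. The last row of the table shows this.

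**The case against.** A reader might infer that the SAP would return a real phenanthrene effect as no change. The documents do not support that, for two reasons. As written, the regression on BaP dose returns nothing about phenanthrene in either direction; the unpaired test appears only after a recoding that the SAP does not mention. Even then the fault is a loss of power, not blindness: a doubling is detected in 63-99% of trials in the four main scenarios.

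The size of the loss also rests wholly on assumed SDs. The protocol's remark on low intra-individual variation points towards a high correlation but gives no number, and at a correlation near 0.12 pairing gains nothing. That objection stands, which is why the two low-correlation rows are shown.

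It can be said, too, that wider limits make a no-change claim harder to support, not easier. That is true if the interval is read. The tilt towards the hypothesised result arises only if non-significance is taken as evidence of no change. A paired test read that way has the same weakness, though with less lost power.

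Finally, the SAP might be meant for data pooled across BaP doses, for instance with protocol 8233. Nothing in the documents says so. If it were, repeated cycles from one person would still not be independent, and the phenanthrene contrast would still be missing.

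None of this rescues the analysis for this study's comparison. The design is paired and the only test is not.

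**Conclusion.** The point holds in a bounded form. As written, the SAP's only significance test cannot estimate the phenanthrene contrast, because its regressor is constant. With the predictor recoded, the test has the wrong error structure for the design. Its true size is below 5%, and its interval wider than 95% coverage requires, whenever a subject's cycles are positively correlated.

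With 7 completers and the four main SD pairs, a true 50% change is found about 14-60% of the time unpaired and 72-99% paired. These figures depend on the assumed SDs, on log-normal data and on complete pairs. A moderate effect is therefore likely to be missed when the correlation is high. Large effects mostly are not, and at correlations of about 0.1-0.2 the choice makes little difference.

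**What to change.** For this study's comparison, replace the regression on BaP dose with a within-subject analysis of each log-transformed pharmacokinetic parameter. Take the mixture-minus-BaP-alone difference per subject, with its t-test and interval on n − 1 df, or fit an equivalent model with condition and subject terms. A subject term added to the present regression is not enough, since the dose column would still be constant.

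State that, for subjects from protocol 8233, the 50 ng BaP-alone cycle from that study is paired with the same subject's mixture cycle here. Report how many pairs arise this way, since they can span up to 12 months.

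Report the mixture/alone ratio with its 95% interval, and say that non-significance will not be read as no change.

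Do not add an additive subject intercept to the through-origin and Michaelis-Menten models in the BIC step. It would remove the constraint that defines the through-origin line.

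The cost is SAP wording. Error df fall from 12 to 6 at n = 7, which is outweighed on interval width once the correlation exceeds about 0.2. Dosing, visits and sample size do not change.
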